4.4.2 Secondary Efficacy Endpoints

For all continuous secondary efficacy endpoints, in addition to the model based analyses, they will also be summarized descriptively at each assessment visit. Analysis populations are specified for each endpoint.

4.4.2.1 Proportions of NEDA patients during the initial 24-week and the initial 48-week period

This endpoint will be analyzed on the mITT population using the same approaches as described above in Section 4.4.1, for the proportion of NEDA patients assessed during the initial 24-week period and during the initial 48-week period.

4.4.2.2 Time to first protocol-defined event of disease activity

The analyses will include patients in the mITT population.

Patients with early study discontinuation before any disease activity event will be censored at the withdraw date, which is defined in Section 4.6.1. It will be imputed as having an event if discontinuation reason is lack of efficacy or death.

1) Kaplan-Meier analysis of time to first protocol-defined event (refer to section 4.4.1), with estimates (Greenwood 95% confidence intervals using a log-log transformation) of proportion of patients with NEDA determined at week 96 and week 104 (or time of the last event/censoring if that is before week 104). Kaplan-Meier plots will be produced up to the last available time of censoring or event.

2) Life-table analysis will be used to estimate the survival probability of time to first protocol-defined event, with estimates and Greenwood 95% confidence intervals using a log-log transformation by using time intervals which correspond to planned MRI assessments (weeks 24, 48 and 96). Thus, exact time of protocol-defined relapses and 24-weeks CDP will fall within MRI time intervals such as [week 8-week 24), [week 24-week 48), [week48-week96) and [week 96, -end of study]. Life-table plots will be produced.

Sample SAS code can be found below (SAS code is regarded as “draft” until fully validated at the analysis stage):

a) Binary method

```
ods output binomial=dataset BinomialTest=tpvalue;  
proc freq data=event ate;  
    tables eventyn / binomial (level='1') alpha=0.05;  
run;
```

b) Kaplan-Meier method

```
proc lifetest data=dataset method=km conftype=loglog outsurv=surv plots=none notable
STDERR;
time aval*eventyn(1);
run;
```

c) Life -Table method

```
proc lifetest data=dataset method=life conftype=loglog intervals=24 48 96 outsurv=surv
plots=none STDERR;
time aval*eventyn(1);
run;
```

4.4.2.3 Change in EDSS from baseline to week 96

EDSS (actual value, change, percentage change from baseline) will be summarized at each visit (up to week 96) for the ITT population. The change in the eight function scores from baseline up to week 96 will also be summarized for the ITT population.

Additionally, summary statistics will also be presented at week 96 for the following categories of change in EDSS:

- worsened (>0.5),
- stable ($-0.5, 0, 0.5$)
- improved (<-0.5)

Change from baseline in EDSS at Weeks 96 will be analyzed using a longitudinal mixed effects model repeated measure (MMRM). The model's fixed effects will include visit along with the following covariates:

- Baseline EDSS (continuous variable),
- Duration since MS Symptom Onset (≤ 3 years, >3 and ≤ 5 years, >5 years and ≤ 10 years, >10 years)",
- Presence of T1 Gd-enhanced lesions at Screening (Yes/No).
- Number of previous DMTs (1, >1)
- Enrollment reasons (relapse only, MRI only or both relapse and MRI)

Visit will be treated as a repeated variable within a patient. Patient and visit will be treated as factor variables. An unstructured variance-covariance structure will be applied to model the within-patient errors. The model will be fitted using the Restricted Maximum Likelihood method (REML). Denominator degrees of freedom will be estimated using Satterthwaite's approximation. If the model doesn't converge, other variance-covariance structures can be considered.

Sample SAS code can be found below (SAS code is regarded as “draft” until fully validated at the analysis stage):

```
proc mixed data=data method=REML;
  class VISIT USUBJID [covariates];
  model change = [covariates] VISIT/ ddfm= satterthwaite;
  repeated VISIT / type=un subject = USUBJID;
  lsmeans VISIT / cl;
  ods output lsmeans = lsm; * contains the adjusted means;
run;
```

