1. A sustained change in EDSS for a minimum of 24 weeks (-2 weeks) from the initial progression event i.e. the change in EDSS must be sustained at all available (scheduled or unscheduled) visits for a minimum of 24 weeks ($\geq 168-14$ days= 154 days) after initial progression. An “Early Discontinuation” visit can be used as a confirmation visit if it falls into the visit window (defined in the protocol) of any scheduled visit. The EDSS assessments (if any) between the initial disability progression and the confirmation of disability progression should be at least as high as the minimum change required for progression.
2. Scheduled visits within 30 days after the onset of a clinical relapse that meets conditions 1, 2 and 3 of a protocol-defined relapse definition cannot be used for confirmation of disability progression. The confirmation of the disability progression must then be based on the EDSS assessment at the next scheduled visit (which is not within 30 days of a protocol defined relapse).
3. If a patient has a missing assessment at the scheduled visit taking place at 24 weeks (≥ 154 days) after an initial progression, the confirmation of the disability progression must be based on the assessment at the next scheduled visit.

For the patients who have the initial progression at week 96 and roll over to the long term extension of Ocrelizumab study, a confirmation EDSS assessment will be collected in the long term extension (Liberto) study.

Patients who complete the treatment period without confirmed progression of disease will be censored at the date of their last EDSS assessment during the treatment period. Patients with an initial assessment of disease progression who subsequently discontinue

from the study without further assessments will not be considered to have confirmed disease progression, if the discontinuation reason is not lack of efficacy or death. Patients who discontinue from the study due to lack of efficacy or death without confirmed progression of disease will be imputed as having an event (i.e., CDP) at the time of discontinuation.

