4.4.2.6 Time to onset of first protocol-defined relapse

This endpoint will be analyzed for patients in the ITT population. All protocol-defined relapses, as defined in section 4.4.1, that occurred during the treatment period will be considered.

Patients who did not experience an event at the end of the treatment period are censored at the last available clinical visit up to week 96. Patients who discontinue from the study due to lack of efficacy or death without confirmed progression of disease will be imputed as having an event at the time of discontinuation.

The Kaplan–Meier methods will be used to estimate the survival function for the time to first protocol-defined event. Kaplan-Meier rates and Greenwood 95% CI using log-log transformation will be presented at 24 weeks, 48 weeks and 96 weeks. Kaplan-Meier plots will be produced.

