4.4.2.8 Time to onset of first new and/or enlarging T2 lesion

This endpoint will not be analyzed as the measurement of T2 lesion by MRI is only performed at week 24, 48 and 96, while the actual onset time can be very different from the MRI visit.

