4.6.1 Exposure of Study Medication

Definitions

Dose: Ocrelizumab dose is given as one infusion or two infusions administered 2 weeks apart. Patients will be considered to have received a Dose of treatment if at least part of one infusion of that Dose (either Day 1 or Day 15 for dual infusions) was given. If a Dose is completely missed instead of delayed, the next dose number will be based on the number of previous doses received.

Treatment duration (in weeks) for a patient will be calculated as follows:

$$[(\text{Date of last contact}^* - \text{Date of first dose}) + 1] / 7$$

Treatment duration (in years) for a patient will be calculated as follows:

$$[(\text{Date of last contact}^* - \text{Date of first dose}) + 1] / 365.25$$

*Earliest 1) date of last contact from the study completion page or study early termination page

2) date of death

3) CCOD

Exposure Analysis

Exposure of ocrelizumab will be summarized using descriptive statistics with the following data:

- treatment duration (weeks),
- number of doses received (day 1 and day 15 infusions are considered as one dose)
- total cumulative dose (mg).

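### SAP 4.4.2.2 closes its life-table intervals on the left at Weeks 24, 48 and 96, so scan events dated on or after those weeks count one interval late, and event-free completers have no stated censoring date

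*SAP*

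**What the plan says.** **Life table (SAP 4.4.2.2).** Intervals are chosen to match the planned scans. Exact event times "will fall within MRI time intervals such as [week 8-week 24), [week 24-week 48), [week48-week96) and [week 96, -end of study". Each interval includes its left end and excludes its right end. The draft code uses the same three cuts with no allowance for visit windows: "method=life conftype=loglog intervals=24 48 96 outsurv=surv".

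**Scan timing (Protocol Appendix 1; SAP Appendix 2).** After the Week-8 reset, scans are due at Weeks 24, 48 and 96, each ±14 days. Footnote r asks sites to try to scan, and to read the scan locally, before the next infusion. Weeks 24 and 48 are infusion visits; Week 96 is not.

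**Kaplan-Meier (SAP 4.4.2.2).** The event-free proportion is "determined at week 96 and week 104 (or time of the last event/censoring if that is before week 104").

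**Censoring (SAP 4.4.2.2).** Only early discontinuers have a date: they are "censored at the withdraw date, which is defined in Section 4.6.1". Section 4.6.1 does not contain that term. It computes treatment duration from the earliest of death, data cut-off and the "date of last contact from the study completion page or study early termination page". The component endpoints do cover completers, but differently. For CDP, patients "will be censored at the date of their last EDSS assessment during the treatment period" (4.4.1). For first relapse, they "are censored at the last available clinical visit up to week 96" (4.4.2.6). SAP 2.4 defines an end of the Treatment Period, which 4.4.2.2 does not invoke.

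**The concern.** A lesion found at the Week-24 visit should count against being event-free at Week 24. With left-closed intervals it does so only if the scan is dated before Week 24. A scan exactly on the nominal day already falls in the next interval, so the rule misplaces events even with perfect visit adherence and defeats the aim of matching intervals to scans.

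The missing completer rule matters because event-free completers are the patients who make up NEDA. Whether they count as surviving the last interval or as withdrawn within it changes the Week-96 figure.

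The SAP sees the dating problem elsewhere. It drops time to first T2 lesion, and likewise time to first T1 Gd lesion, because "the actual onset time can be very different from the MRI visit". The composite contains the same MRI events but has no rule for dating them.

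At stake is a listed secondary endpoint and its repeat for clinical relapses in SAP 4.4.4. Binary, Kaplan-Meier and life-table NEDA for the same week could disagree because of scan dates and interval conventions rather than disease activity.

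**Working it through.** **Plan's own figure.** Section 4.4.2.2 states no numerical result. SAP 2.3 gives 750 patients and 30% NEDA, with a 95% CI of 26.7% to 33.4%. Clopper-Pearson for 225/750 gives 26.74% to 33.42%, half-width 3.34 points. For 375/750 the half-width is 3.64. The stated figures reproduce to rounding, and 3.3 points serves as a yardstick below.

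**Week 24, general form.** Let S be the proportion event-free just before the scan, q the chance that the scan shows a first event, and f the share of those events dated on or after Week 24. The correct value is S(1 − q). The SAP's cut gives S(1 − fq). The error is f × S × q. With S = 0.95 (assumed):

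| f | q = 2% | q = 5% | q = 10% |
|---|---|---|---|
| 0 | 0 | 0 | 0 |
| 0.25 | +0.5 | +1.2 | +2.4 |
| 0.5 | +1.0 | +2.4 | +4.8 |
| 1 | +1.9 | +4.8 | +9.5 |

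**Worked life table.** From the SAP: N = 750 and NEDA about 30%. Assumed: half of first events are MRI-detected (87 at each of three scans), 263 clinical events are spread evenly over 96 weeks, and there is no dropout. That leaves 226 event-free. Scan dates are all before the nominal day, uniform over ±14 days (15/29 = 52% on or after it, 45 of 87), or all on or after it. Completers are counted as surviving to Week 96.

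| Rule | Week 24 | Week 48 | Week 96 |
|---|---|---|---|
| Scan events at scheduled visit (same as all scans early) | 598/750 = 79.7% | 445/750 = 59.3% | 226/750 = 30.1% |
| SAP cuts, 52% on or after | 643/750 = 85.7% | 490/750 = 65.3% | 271/750 = 36.1% |
| SAP cuts, all on or after | 685/750 = 91.3% | 532/750 = 70.9% | 313/750 = 41.7% |

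The errors are 45/750 = 6.0 and 87/750 = 11.6 points. With an MRI share of 30% or 70% and 52% on or after, the Week-24 errors are 27/750 = 3.6 and 64/750 = 8.5 points. If only Week-96 scans are late (52%), the error is 0 at Weeks 24 and 48 and +6.0 at Week 96.

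**Week 96 and completers.** The life table uses n − c/2 as the effective number at risk, where c is the number censored in the interval. In the 52% case, 490 enter the last interval before Week 96 and 219 have events in it.

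- No completer censored before Week 96: 0.6533 × (1 − 219/490) = 36.1%.
- 113 censored before: 0.6533 × (1 − 219/433.5) = 32.3%.
- All 226 censored before: 0.6533 × (1 − 219/377) = 27.4%.

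The correct value is 30.1%, so the sign depends on a rule that is not stated. With all scans early and all completers censored before Week 96, the result is 0.5933 × (1 − 219/332) = 20.2%.

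**Kaplan-Meier.** At Week 96 it misses only scans dated after the nominal day. In the example, with everyone still at risk at Week 96, that is 87 × 14/29 = 42 events, or 42/750 = 5.6 points. The Week-104 estimate recovers them if completers stay at risk past the window. If completers are instead censored at their own visit, with visits uniform over 29 days, the large-sample factor for the Week-96 scan is the product over k = 1 to 29 of (1 − q/k), where 1 − q is wanted. For q = 0.02, 0.05 and 0.12 this is 0.924, 0.819 and 0.614, against 0.98, 0.95 and 0.88.

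**The case against.** The interval sentence has relapses and CDP as its subject, offers the intervals as examples, and sits beside code marked as draft. It does not say that MRI events are dated by scan day. This stands as a reason for restraint, but it does not remove the problem. The life table is for the composite, and dating an MRI event at nominal Week 24 would also place it in the later interval under left closure.

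The scan-before-infusion request makes early scans likely at exactly Weeks 24 and 48. This stands. A reader might infer that every Week-24 and Week-48 scan event moves; the documents do not support that, because earlier scans stay in the right interval and the bias may be small or nil there.

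The Week-104 read-out, and a final interval running to the end of the study, suggest follow-up past Week 96. SAP 2.4 suggests instead that the Treatment Period ends with the last Week-96 efficacy measurement. Neither is named as the completer censoring date, so the large downward Kaplan-Meier errors hold under one reading only.

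Because SAP 4.4.4 equates Week 8 with study day 57, a reader might infer that time is study day divided by 7, so that Kaplan-Meier at Week 96 would miss even on-time scans. The documents do not support that: a relapse cut-off does not define the time scale, and SAP 4.4.2.4 defines time to CDI in days from baseline. On elapsed days, an on-time scan is counted.

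Finally, the study is descriptive and single-arm, and the life table is a second presentation of one secondary endpoint. This stands and limits the importance.

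**Conclusion.** The point holds in limited form. Left closure at the scan weeks raises life-table NEDA at Weeks 24 and 48 whenever scan events are dated on or after the nominal week, and leaves it unbiased when all are earlier. A reader might infer that Week 96 also reads too high. It may, but it may also read too low, depending on the unstated completer rule. The undefined withdrawal date is a separate gap that needs correcting.

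The documents give no MRI event rates, scan dates or MRI share of first events, so no single size can be quoted. Under the assumptions shown, the Week-24 error runs from 0 to several points, and above 10 only if MRI events are common and almost all scans fall on or after the nominal day. Some of these values exceed the planned half-width of 3.3 points.

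A reader might also infer that the primary result is inflated. It is not: the primary NEDA (SAP 4.4.1) and the Week-24 and Week-48 proportions (4.4.2.1) are binary and use no life-table intervals. Severity is minor to moderate, confined to the secondary time-to-event analysis and its repeat in 4.4.4.

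**What to change.** In SAP 4.4.2.2:

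- Assign each MRI-detected event to its scheduled visit, and use right-closed intervals (0–24], (24–48] and (48–96]. Start at 0 because clinical events count from baseline (Protocol 6.4.4).
- State one censoring rule that keeps event-free completers at risk until all Week-96-visit events are counted, for example nominal Week 96 with events ordered before censoring. In the life table, count completers as surviving the last interval, not as withdrawn within it.
- Replace the reference to Section 4.6.1 with an actual definition of the withdrawal date.
- Align the draft code, and carry the same rules into the repeat in 4.4.4.

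Merely moving the cuts 14 days later is not enough. In the worked example, completers are then censored inside the last interval, and the estimate becomes 0.5853 × (1 − 213/326) = 20.3%, against 30.1%.

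The cost is SAP wording and a derived time variable, with no new data. The downside is slightly coarser event dating.

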4.4.2.4 Proportion of patients who have CDI

This endpoint will be analyzed on the ITT population.

For patients with a baseline EDSS score ≥ 2 , disability improvement is defined as a reduction in EDSS score ≥ 1.0 compared to baseline EDSS score. The same approach to data derivation of CDP will be used for the derivation of CDI, in particular the confirmation of the disability improvement at 24 weeks. For patients with baseline EDSS score < 2 , CDI will not be defined.

The proportion of patients who, over a 96-week period, have CDI will be presented along with a two-sided 95% Clopper-Pearson exact confidence interval.

Additionally, for patients with a baseline EDSS score ≥ 2 , the time to CDI will be defined as the number of days from baseline to CDI. The Kaplan–Meier method will be used to estimate the survival function for the time to CDI. Kaplan-Meier rates and Greenwood 95% CI using log-log transformation will be presented at 24 weeks, 48 weeks and 96 weeks. Kaplan-Meier plots will be produced.

4.4.2.5 Annualized rate of protocol-defined relapses at Week 96

This endpoint will be summarized for the ITT population.

The unadjusted annualized protocol-defined relapse rate will be defined as the total number of protocol-defined relapses for all patients divided by the total years of drug exposure (defined as the length of treatment period).

In addition, the adjusted annualized relapse rate will be estimated using a negative binomial model, adjusting for:

- Duration since MS Symptom Onset (≤ 3 years, >3 and ≤ 5 years, >5 years and ≤ 10 years, >10 years),
- presence of T1 Gd-enhanced lesions at Screening (Yes/No),
- presence of relapses prior screening as per CRF (Yes/No)
- number of previous DMTs (1, >1)

and including the log-transformed years of drug exposure time (in years) as an “offset” variable. The adjusted rates along with the two-sided 95% confidence interval will be presented.

Sample SAS code can be found below (SAS code is regarded as “draft” until fully validated at the analysis stage):

```
proc genmod data=ARR;
  class [covariates];
  model N_PDR = [covariates]/offset=EXPLOG link=log dist=negbin type3;
  estimate “Annualized rate” intercept 1 DISDUR xx xx T2VOL <mean value >
T1GD xx xx RELAPSE xx xx PDMT xx xx/ exp cl;
  ods output ParameterEstimates=est;
run;
```

As sensitivity analyses, the analyses specified above will be repeated on the annualized rate of clinical relapses at Week 96 (see section 4.4.4).

4.4.2.6 Time to onset of first protocol-defined relapse

This endpoint will be analyzed for patients in the ITT population. All protocol-defined relapses, as defined in section 4.4.1, that occurred during the treatment period will be considered.

Patients who did not experience an event at the end of the treatment period are censored at the last available clinical visit up to week 96. Patients who discontinue from the study due to lack of efficacy or death without confirmed progression of disease will be imputed as having an event at the time of discontinuation.

The Kaplan–Meier methods will be used to estimate the survival function for the time to first protocol-defined event. Kaplan-Meier rates and Greenwood 95% CI using log-log transformation will be presented at 24 weeks, 48 weeks and 96 weeks. Kaplan-Meier plots will be produced.

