4.2 ANALYSIS OF STUDY CONDUCT

Patient disposition information will be summarized as follows:

- Number of patients enrolled
- Number of patients in the ITT population and PP population
- Number of patients who complete study treatment
- Number of patients who discontinue study treatment and the reasons for study treatment discontinuation
- Number of patients who discontinue study and the reasons for study discontinuation
- Number of patients entering the safety follow-up
- Number of patients who roll over to the long term extension of Ocrelizumab study
- Number of patients who received any DMT (Disease modifying treatment) after Ocrelizumab discontinuation

Major protocol violations, including violations of inclusion/exclusion criteria collected during the study via PDMS will be summarized and listed.

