4.4 EFFICACY ANALYSIS

4.4.1 Primary Efficacy Endpoint

Protocol-defined event definition

The definition of a protocol-defined event of disease activity is the occurrence of at least one of the following individual events while on treatment with ocrelizumab:

- A protocol-defined relapse defined as an occurrence of new or worsening neurological symptoms attributable to MS. Symptoms must persist for > 24 hours and should not be attributable to confounding clinical factors (e.g., fever, infection, injury, adverse reactions to medications), and immediately be preceded by neurological stability for at least 30 days.
- 24-weeks CDP based on increase in EDSS while on treatment with ocrelizumab
- A new T1 Gd-enhanced lesion on MRI after week 8
- A new and/or enlarging T2 hyperintense lesion on MRI after week 8

The MRI activity will be calculated on the events starting from week 8 (baseline reset).

Patient without any of this protocol-defined event of disease activity will be considered as NEDA = Yes (no evidence of disease activity).

The primary endpoint, NEDA, as well as the related disease activities components and combinations listed below, will be evaluated on the mITT population based on the following analysis principles:

- Patients, who discontinued treatment prior week 96 due to death or lack of efficacy, will be considered as having evidence of disease activity at the time of treatment discontinuation (e.g NEDA="NO", Relapse="Yes" and CDP="Yes").
- Patients who discontinued treatment for reasons other than death or lack of efficacy with no evidence of disease activity at the time of early treatment discontinuation will be excluded from the analysis as their disease activity status cannot be ascertained.

This is further summarized in the table below:

Endpoint	Patients who discontinued treatment without related disease activities prior week 96 due to:	
	death or lack of efficacy	Other reason than death or lack of efficacy with no evidence of disease activity
NEDA	included with evidence of disease activity (NEDA=NO)	excluded
Relapse	included with evidence of disease activity (Relapse=Yes)	excluded

24-weeks CDP	included with evidence of disease activity (CDP="Yes")	
 • If discontinuation before confirmation, excluded • If discontinuation after confirmation, included when CDP="Yes"
T1 Gd-enhanced lesions after week 8	included with evidence of disease activity	excluded

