4.4.2.7 Time to onset of 24 weeks CDP

This endpoint will be analyzed for patients in the ITT population. All 24-weeks CDP that occurred during the treatment period will be considered.

Patients without a 24-Week CDP will be censored at the last EDSS assessment. Patients who discontinue from the study due to lack of efficacy or death without confirmed progression of disease will be imputed as having an event at the time of discontinuation.

This endpoint will be analyzed using the same approach as described above in Section 4.4.2.6.

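### SAP 4.4.2.6 makes the imputation of a first relapse depend on confirmed disability progression instead of on relapse

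*SAP*

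**What the plan says.** **Time to first relapse (SAP 4.4.2.6, ITT).** Patients without an event "are censored at the last available clinical visit up to week 96". Those whose study participation ends "due to lack of efficacy or death without confirmed progression of disease will be imputed as having an event at the time of discontinuation". Survival methods of the Kaplan-Meier type then "estimate the survival function for the time to first protocol-defined event", which is the name of the composite endpoint of 4.4.2.2.

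**Time to 24-week CDP (SAP 4.4.2.7, ITT).** Here too, those whose study participation ends "due to lack of efficacy or death without confirmed progression of disease will be imputed as having an event". In this section the condition names the section's own endpoint.

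**Binary analysis (SAP 4.4.1, mITT).** NEDA and its "components and combinations listed below, will be evaluated on the mITT population based on the following analysis principles". Under the first principle, where death or lack of efficacy ends treatment before week 96, patients "will be considered as having evidence of disease activity at the time of treatment discontinuation (e.g NEDA='NO', Relapse='Yes' and CDP='Yes". The table that follows is headed "Patients who discontinued treatment without related disease activities prior week 96 due to", and its relapse line sets Relapse to Yes for these patients without mentioning CDP. Patients who stop for other reasons with no activity are excluded.

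**CDP proportion.** SAP 2.2.2 lists the 96-week proportion with disability improvement (CDI), CDP or stable disability as a secondary endpoint. The matching method section, 4.4.2.4, describes CDI only.

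**The concern.** An imputation rule for time to first relapse should ask whether the patient has already had a relapse. The rule in 4.4.2.6 asks whether the patient has had confirmed progression. The relapse curve would then depend on a different component of NEDA, and in the wrong direction: among relapse-free patients who leave for lack of efficacy or death, those with documented progression are treated as relapse-free up to censoring, and those without it are given a relapse.

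Two analyses of the same event would also classify the same patient differently. SAP 4.4.4 repeats 4.4.2.6 for all reported clinical relapses, and 4.4.5 repeats the secondary endpoints in subgroups, so the rule carries into those outputs. A programmer who follows the text gets the wrong result; one who follows the evident intent departs from the SAP.

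**Working it through.** The plan states no figure on this point, so the check is mainly a comparison of rules. The only numerical inputs from the documents are the planned 750 patients (SAP 2.3) and the minimum subgroup size of 50 (SAP 4.4.5).

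**1. Meaning of the condition.** The last sentence of the CDP definition in SAP 4.4.1 uses the same phrase and identifies the imputed event as CDP. Confirmed progression therefore means 24-week CDP and cannot be read as relapse.

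**2. Parallel rules.** SAP 4.4.2.2 imputes an event only where no disease activity event has yet occurred, which is its own endpoint. SAP 4.4.2.7 also conditions on its own endpoint. Of the three time-to-event rules, only 4.4.2.6 conditions on another endpoint.

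**3. Four patients.** Each leaves both treatment and study before week 96 for lack of efficacy or death.

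| Relapse observed | CDP confirmed | 4.4.1 relapse row | 4.4.2.6 as written | 4.4.2.6 conditioned on relapse |
|---|---|---|---|---|
| No | No | Yes | Event, imputed | Event, imputed |
| No | Yes | Yes | Censored | Event, imputed |
| Yes | No | Yes | Event, observed | Event, observed |
| Yes | Yes | Yes | Event, observed | Event, observed |

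Only the second line changes. Where a relapse was observed, it precedes discontinuation and is the first event in any case.

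**4. The trigger.** Now take a relapse-free patient who stops treatment for lack of efficacy but stays in the study. Protocol 3.1.4 and 4.6.2 provide for this: early treatment discontinuers go into follow-up of at least 96 weeks. SAP 4.2 also tabulates the two kinds of stopping separately, the first being "Number of patients who discontinue study treatment and the reasons for study treatment discontinuation". Under 4.4.1 this patient is positive for relapse and CDP. Under 4.4.2.6 and 4.4.2.7, and under the closing sentence of the CDP definition, the trigger is leaving the study, so nothing is imputed and the patient is censored. Correcting the condition in 4.4.2.6 leaves this difference in place.

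**5. Size for time to relapse.** Let R be the number at risk when the patient discontinues. Counting the patient as an event instead of censored lowers the week-96 estimate S(96) by S(96)/R. With no other censoring, R = N × S(t−), so the reduction is S(96)/(N × S(t−)), which is at most 1/N.
- Whole study: 1/750 = 0.13 point per patient. An assumed 1 to 5 such patients gives at most 0.13 to 0.67 point (5/750).
- Subgroup of 50: 1/50 = 2 points per patient.

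Other censoring before that time shrinks R and makes the effect somewhat larger.

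**6. Size for the optional CDP row.** Let x be observed confirmed events and k the lack-of-efficacy or death discontinuers without one. The imputed proportion is (x + k)/750; counting the k as non-events gives x/750; the difference is k/750. All counts here are assumptions.
- x = 75: 10.00% observed; 80/750 = 10.67% with k = 5; 115/750 = 15.33% with k = 40.
- x = 8, as for a rare overlap row: 1.07% observed; 13/750 = 1.73% with k = 5; 48/750 = 6.40% with k = 40.

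The actual mITT denominator will differ from 750.

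**The case against.** The best defence is that this is a copying slip with an obvious intent. The heading and opening paragraph of 4.4.2.6 fix the endpoint as protocol-defined relapse, the study is exploratory and mainly descriptive (Protocol 6), and very few patients can be affected. The point about size stands. The point about intent does not remove the error: SAP 4 says its analyses supersede the protocol's, and SAP 4.7 says missing data are handled section by section, so the section's own wording governs.

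On the trigger, it can be argued that treatment and study discontinuation are used loosely. Appendix 1 note a of the protocol starts follow-up at discontinuation from the study, whereas section 3.1.4 starts it after the early treatment discontinuation visit. If the two are meant to be the same, the SAP needs to say so.

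A reader might infer that no observed CDP proportion is planned at all. The documents do not support that. SAP 2.2.2 lists a CDP proportion, and SAP 4.7 imputes nothing unless specified. The imputing sentence in the CDP definition sits in a paragraph about censoring and event times, so whether it governs this proportion is arguable. The supportable statement is that the method is not specified. Nor is the imputed share hidden: disposition by reason bounds it from above, and the 4.4.1 row for patients who stopped for lack of efficacy or death with no earlier event bounds it from below.

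**Conclusion.** The rule in 4.4.2.6 is wrong as written. Its condition belongs to 4.4.2.7, and applied literally it gives a result that contradicts the relapse row of 4.4.1 for one type of patient: discontinued for lack of efficacy or death, CDP confirmed, no protocol-defined relapse. The number of such patients is unknown, because the documents give no discontinuation rate by reason, but it is likely to be small. The figures above rest on 750 patients, assumed counts and, for the curve, no other censoring.

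Two stronger readings should be resisted. One is that the primary result is affected: it is not, since 4.4.2.6 does not feed NEDA and these patients are NEDA failures under 4.4.1 either way. The other is that rewording 4.4.2.6 makes it agree with the 4.4.1 relapse row. It does not, because the triggers differ. Even with one trigger, differences will remain from mITT versus ITT and from excluding versus censoring patients who stop for other reasons.

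The CDP proportion is a minor, optional matter of reporting.

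**What to change.** 1. In SAP 4.4.2.6, change the imputation condition from absence of confirmed progression to absence of a protocol-defined relapse, and name time to first protocol-defined relapse in the Kaplan-Meier sentence. Leave the condition in 4.4.2.7 as it is.
2. State one trigger, either stopping treatment or leaving the study, for the 4.4.1 principles, the closing sentence of the CDP definition, 4.4.2.6 and 4.4.2.7, so that the binary and time-to-event analyses of relapse and CDP classify the same patient alike. Note that the differences in population and in censoring are intended.
3. Optional: in 4.4.2.4, give a method for the CDP proportion listed in 2.2.2, using observed confirmed events only and counting lack-of-efficacy or death discontinuers without the event as non-events. Excluding them while keeping those with the event would make inclusion depend on outcome. If wanted, do the same for the three rows in 4.4.1 that require two kinds of activity together. Show these beside the imputed rows, which stay.

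The cost is two phrases, a sentence or two on the trigger and, if item 3 is taken up, a few table rows. No new data are needed.
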